#### 6.1.1. Administration

AD treatable areas will be all areas affected by AD, except hair-bearing scalp.

PsO treatable areas will be all areas affected by PsO, except hair-bearing scalp, palms, soles, fingernails, and toenails.

A layer of study intervention ointment will be applied at a target application rate of approximately 3 mg/cm^2 by using a fingertip unit method.

### Day 1 Visit

At the Day 1 visit, before the Day 1 initial study intervention application is performed, the designated areas for treatment will be identified and documented in the participant's source document study records (body map). The participant and/or caregiver will be provided with a paper version of the body map.

Participants and/or caregivers will be encouraged to observe and participate in the initial study intervention application on Day 1.

### Post Day 1

Following Day 1 visit through the final dose at Week 12 visit, the study intervention should be applied once daily (around same time of the day), to all treatable AD or PsO involved areas identified at the Day 1 visit as well as to new areas identified as "treatable" during the course of 12 weeks. All participants will be supplied with instructions on application.

- Note: Any new AD or PsO areas identified by the participant or caregiver(s) should also be treated with the study intervention *after assessment by the investigator or his/her designee*. An unscheduled visit for assessment of the new lesion may be required at the discretion of the Investigator. If the new lesion is identified as treatable, then body map will be updated, and study intervention need will be re-assessed.

The study intervention will be applied at home/residence except on the days of in-clinic visits. **On the days of scheduled in-clinic visit, participants will be instructed to refrain from applying the study intervention at home/residence.** The last dose of study intervention will be applied during the Week 12 in-clinic visit (EOT visit) as specified in the **SoA**.

- Note: If due to public emergency, local regulations don't allow participant to visit the clinic on scheduled visit days, the participant will refrain from applying the study intervention until selected assessments can be completed using televisit or home health visit.

The participant and/or caregiver will be instructed to complete the dosing diary section of the e-diary, starting with the first dose applied in the clinic on Day 1 through Week 12 (each time study intervention is applied). If a participant misses applying a dose, the participant should apply this dose provided this dose should have been applied within the last 6 hours. For longer intervals, the dose should be skipped. The missed dose should be recorded in the dosing diary. The next dose should be applied according to the regular dosing regimen.

**Treated area identified on Day 1 should continue to be treated even if substantial improvement or clearing of AD or PsO occurs.**

The reason for maintaining study intervention treatment areas the same as identified at Day 1 is to understand the efficacy, systemic safety, and local tolerability of PF-07038124 ointment when applied to for 12 weeks in participants with AD or PsO.

Under no circumstances will the study intervention application regimen be modified (eg, frequency of application increased or reduced, not stopped, or the application rate [target 3 mg/cm^2] increased or reduced) during the study. Temporary discontinuation of study intervention may be appropriate under some circumstances (eg, surgery, non-serious infections) and should be discussed with the medical monitor (or designee) preferably prior to temporary discontinuation of the study intervention.

Study intervention administration details will be recorded on the CRF.

## 6.2. Preparation, Handling, Storage, and Accountability

1. The investigator or designee must confirm appropriate temperature conditions have been maintained during transit for all study interventions received and any discrepancies are reported and resolved before use of the study intervention.
2. Only participants enrolled in the study may receive study intervention and only authorized site staff may supply or administer study intervention. All study interventions must be stored in a secure, environmentally controlled, and monitored (manual or automated recording) area in accordance with the labeled storage conditions with access limited to the investigator and authorized site staff. At a minimum, daily minimum and maximum temperatures for all site storage locations must be documented and available upon request. Data for nonworking days must indicate the minimum and maximum temperatures since previously documented for all site storage locations upon return to business.
3. Any excursions from the study intervention label storage conditions should be reported to Pfizer upon discovery along with any actions taken. The site should actively pursue options for returning the study intervention to the storage conditions described in the labeling, as soon as possible. Once an excursion is identified, the study intervention must be quarantined and not used until Pfizer provides permission to use the study intervention. Specific details regarding the definition of an excursion and information the site should report for each excursion will be provided to the site in the IP manual.
4. Any storage conditions stated in the SRSD will be superseded by the storage conditions stated on the label.
5. Study interventions should be stored in their original containers.
6. Site staff will instruct participants on the proper storage requirements for take-home study intervention.

7. The investigator, institution, or the head of the medical institution (where applicable) is responsible for study intervention accountability, reconciliation, and record maintenance (ie, receipt, reconciliation, and final disposition records), such as the IPAL or sponsor-approved equivalent. All study interventions will be accounted for using a study intervention accountability form/record. All study intervention that is taken home by the participant, both used and unused, must be returned to the investigator by the participant. Returned study intervention must not be redispatched to the participants.
8. Further guidance and information for the final disposition of unused study interventions are provided in the IP manual. All destruction must be adequately documented. If destruction is authorized to take place at the investigator site, the investigator must ensure that the materials are destroyed in compliance with applicable environmental regulations, institutional policy, and any special instructions provided by Pfizer.

Upon identification of a product complaint, notify the sponsor within 1 business day of discovery IP manual.

#### **6.2.1. Preparation and Dispensing**

Within this protocol, preparation refers to the investigator site activities performed to make the study intervention ready for application or dispensing to the participant/caregiver by qualified staff.

Dispensing is defined as the provision of study intervention, concomitant treatments, and accompanying information by qualified staff member(s) to a healthcare provider, participant, or caregiver in accordance with this protocol. Local health authority regulations or investigator site guidelines may use alternative terms for these activities.

The study intervention will be dispensed in a blinded fashion using an IRT system at Day 1/Baseline, Week 1, Week 2, Week 4, Week 6, Week 8 and Week 10 visits. A qualified staff member will dispense the study intervention via unique container numbers on the cartons provided, in quantities appropriate for the study visit schedule and the treatable % BSA.

For doses to be applied at home, the participant or caregiver should be instructed to maintain the product in its original package provided throughout the course of dosing and return the product and its original package (including empty, partial used and unused tubes) to the site at the next study visit.

Study intervention will be assigned to participants at the Day 1 visit once the participant is successfully randomized through the IRT system. The investigator, appropriate delegate or site personnel will access the IRT system at Screening and all subsequent study intervention dispensing visits to enter information including, but not limited to, % affected BSA, height, and weight to receive correct tube numbers to be dispensed to the participant. Alternatively,

the tool to standardize the study intervention need calculation across participants and study sites may be provided by the sponsor.

The calculation of treatable %BSA is described in [Section 10.12.1.3](#) and [Section 10.12.2.3](#) for AD and PsO, respectively.

All tubes of investigational product dispensed or returned will be recorded and documented.

### **6.2.2. Study Intervention Accountability**

The investigator site must maintain adequate records documenting the receipt, use, loss, or other disposition of the study intervention supplies. All study intervention will be accounted for using a drug accountability form/record. All tubes of the study intervention must be returned to the investigator by the participant at every visit and at the end of the trial.

The participant will be asked to bring all dispensed study intervention (including empty, partially used and unused tubes) at every visit; participants will be asked to bring e-diary to the clinic at every clinic visit. All previously dispensed study intervention tubes will be retained by the site. For each participant, study intervention tubes with caps will be weighed individually by the study site before dispensing and after return and the weights will be recorded. The sponsor will use the recorded weights to estimate usage (eg, mg/cm^2/application) for each participant. Note that the weight recorded on the study intervention label is a nominal weight and not an exact weight of the study intervention and tube. Detailed drug accountability records, including tube weights measured in the clinic, will be maintained by study staff for each participant.

The original study intervention accountability log, or equivalent document, must be accurately completed, signed by the investigator, and retained at the study site (with a copy supplied to the sponsor) when the study is complete.

### **6.2.3. Destruction of Study Intervention Supplies**

For all study intervention returned to the investigator by the participant, the investigator will maintain the returned supply until destruction is authorized.

The sponsor or designee will provide guidance on the destruction of unused study intervention (eg, at the site). If destruction is authorized to take place at the investigator site, the investigator must ensure that the materials are destroyed in compliance with applicable environmental regulations, institutional policy, and any special instructions provided by Pfizer, and all destruction must be adequately documented.

Further guidance and information for the final disposition of unused study interventions are provided in the IP manual.

### **6.3. Measures to Minimize Bias: Randomization and Blinding**

#### **6.3.1. Allocation to Study Intervention**

Allocation of participants to treatment groups will proceed through the use of an IRT system (IWR). The site personnel (study coordinator or specified designee) will be required to enter or select information including but not limited to the user's ID and password, the protocol number, and the participant number. The site personnel will then be provided with a treatment assignment, randomization number, and DU or container number when study intervention is being supplied via the IRT system. The IRT system will provide a confirmation report containing the participant number, randomization number, and DU or container number assigned. The confirmation report must be stored in the site's files.

Study intervention will be dispensed at the study visits summarized in the [SoA](#).

Returned study intervention must not be re-dispensed to the participants.

The study-specific IRT reference manual and IP manual will provide the contact information and further details on the use of the IRT system.

#### **6.3.2. Breaking the Blind**

The IRT will be programmed with blind-breaking instructions. In case of an emergency, the investigator has the sole responsibility for determining if unblinding of a participant's treatment assignment is warranted. Participant safety must always be the first consideration in making such a determination. If the investigator decides that unblinding is warranted, the investigator should make every effort to contact the sponsor prior to unblinding a participant's treatment assignment unless this could delay further management of the participant. If a participant's treatment assignment is unblinded, the sponsor must be notified within 24 hours after breaking the blind. The date and reason that the blind was broken must be recorded in the source documentation and CRF.

The study-specific IRT reference manual and IP manual will provide the contact information and further details on the use of the IRT system.

### **6.4. Study Intervention Compliance**

Participants will be instructed to bring to the clinic all used, partially used and empty study intervention tubes in their original containers for weighing, at each visit.

Participant compliance with study intervention will be assessed on visits identified in the [SoA](#). Compliance will be assessed by review of the participant/caregiver completed dosing diary section of the e-diary and thorough review of dosing instructions at every visit. The difference in weight(s) of the returned study intervention tubes will be used to estimate the doses applied at the end of the study. Source documents will be placed in the participant's study file. Deviation(s) from the prescribed dosage regimen should be recorded in the CRF.

From Day 1 through Week 12 visit, non-compliance is defined as application of study intervention less than 80% in a week or more than 120% of study intervention applications. If non-compliance is identified, or even if a few dose applications are missed or over-applied (as informed by the participant to the site staff), then, participants will be re-trained on the importance and the process of proper study intervention application. If non-compliance persists, the investigator, in consultation with the sponsor, may withdraw any participant from the study for reasons of non-compliance with the dosing regimen. Investigators should indicate on the appropriate CRF page noncompliance with study intervention and provide an explanation.

Inventory control of all study intervention must be rigorously maintained throughout the duration of the study until all medication has been accounted for and/or returned to the sponsor. Any discrepancies noted between drug dispensing records and the drug inventory must be reported to Pfizer.

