## 7. DISCONTINUATION OF STUDY INTERVENTION AND PARTICIPANT DISCONTINUATION/WITHDRAWAL

### 7.1. Discontinuation of Study Intervention

It may be necessary for a participant to permanently discontinue study intervention. Reasons for permanent discontinuation of study intervention include the following: Liver injury, ECG changes, pregnancy, local tolerability, and AEs.

Note that discontinuation of study intervention does not represent withdrawal from the study. If study intervention is permanently discontinued, the participant will remain in the study to be evaluated for safety. See the [SoA](#) for data to be collected at the time of discontinuation of study intervention and follow-up for any further evaluations that need to be completed.

In the event of discontinuation of study intervention, it must be documented on the appropriate CRF/in the medical records whether the participant is discontinuing further receipt of study intervention or also from study procedures, posttreatment study follow-up, and/or future collection of additional information.

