##### Atopic Dermatitis:

Treatment condition: received treatment: PF-07038124 ointment 0.01%, 0.03% or vehicle, without the benefit of additional prohibited medications and regardless of treatment compliance.

Population: Participants with mild or moderate AD as defined by the inclusion and exclusion criteria.

Variables: Proportion of participants achieving IGA score of clear (0) or almost clear (1) and a reduction from baseline of  $\geq 2$  points at Week 12 and other binary endpoints.

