##### Psoriasis:

Treatment condition: received treatment: PF-07038124 ointment 0.01%, 0.03%, 0.06% or vehicle, without the benefit of additional prohibited medications and regardless of treatment compliance.

Population: Participants with mild, moderate, or severe PsO as defined by the inclusion and exclusion criteria.

Variables: Proportion of participants with PGA score clear (0) or almost clear (1) and a reduction from baseline of  $\geq 2$  points at Week 12 and other binary endpoints.

Inter-current Events: A) Prohibited medication – response will be considered as failure for time points after start date of the event for participants who receive prohibited medication post-randomization. B) Withdrawal and all other events, except COVID-19 pandemic, leading to missing data will be treated similarly assuming that participants no longer receive

benefit from the study intervention and hence will be considered as failure. C) COVID-19 pandemic: if a participant misses a visit due to COVID-19, he/she will be excluded from the analysis for that visit; If a participant discontinues treatment or withdraws from the study due to COVID-19, he/she will be excluded from the analyses after the treatment discontinuation visit or study withdrawal visit, respectively. D) Inadequate compliance – participants data will be used as recorded.

Population level summary: The difference in success rates between each dose level and vehicle.

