## **6. ANALYSES AND SUMMARIES**

### **6.1. Primary Endpoint(s)**

#### **6.1.1. Main Analysis**

- Estimand strategy: Primary Estimand ([Section 2.2.1](#)). This estimand is intended to provide an estimate of the treatment effect in the absence of prohibited medication use in a population that may or may not be fully compliant with the treatment.
- Analysis set: ITT Analysis Set ([Section 4](#)).

- Analysis methodology: A landmark analysis of the IGA/PGA success endpoints at Week 12 will be performed using the ITT analysis set. The proportions responding and the corresponding risk difference comparing active treatment arm to vehicle group will be analyzed using the unconditional exact method; the risk differences and the corresponding 2 sided unconditional exact 95% confidence intervals will be computed using Chan and Zhang (1999) method. The overall family wise Type I error rate will be controlled at the 1 sided 0.025 level using the Hochberg step up procedure.
- Intercurrent events and missing data: A) Prohibited medication – response will be considered as failure for time points after start date of the event for participants who receive prohibited medication post randomization. B) Withdrawal and all other events, except COVID-19 pandemic, leading to missing data will be treated similarly assuming that participants no longer receive benefit from the study intervention and hence will be considered as failure. C) COVID-19 pandemic: if a participant misses a visit due to COVID-19, he/she will be excluded from the analysis for that visit; If a participant discontinues treatment or withdraws from the study due to COVID-19, he/she will be excluded from the analyses after the treatment discontinuation visit or study withdrawal visit, respectively. D) Inadequate compliance – participants data will be used as recorded.
- Proportions, risk differences and 95% confidence intervals will be presented.

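### Protocol 6.4 permits withdrawal from the study for persistent non-compliance, so a conduct rule can decide whether a Week 12 outcome counts, although both estimands are defined irrespective of compliance

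*Protocol*

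**What the plan says.** **Estimand.** Protocol 9.1.1.1 and 9.1.1.2, repeated in SAP 2.2.1 and 2.2.2, define the treatment condition as "without the benefit of additional prohibited medications and regardless of treatment compliance". Event D for both estimands reads "Inadequate compliance – participants data will be used as recorded". SAP 6.1.1 and 6.2.2 repeat event D.

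**Missing outcomes.** For the binary endpoints, event B in SAP 6.1.1 reads "Withdrawal and all other events, except COVID-19 pandemic, leading to missing data will be treated similarly", and the result is a failure. SAP 5.3.1 sets all missing binary values to failure, apart from those due to COVID-19. For the continuous endpoints, SAP 6.2.2 imputes missing active-arm values from a model fitted to the vehicle arm.

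**Conduct.** Protocol 6.4 states that "non-compliance is defined as application of study intervention less than 80% in a week or more than 120% of study intervention applications". The first response is re-training. If the problem persists, "the investigator, in consultation with the sponsor, may withdraw any participant from the study for reasons of non-compliance with the dosing regimen".

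**Leaving treatment versus leaving the study.** Protocol 7.1 notes that "discontinuation of study intervention does not represent withdrawal from the study", but the only purpose it names for keeping such participants is safety evaluation. Its listed reasons for permanent discontinuation do not include non-compliance. Nor do the example reasons for leaving the study in 7.2. Section 7.2.1 keeps participants who ask to stop treatment in follow-up unless they withdraw consent.

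**The concern.** The estimand asks what happens at Week 12 to everyone assigned to an arm, however well they applied the ointment. That needs a Week 12 assessment on non-compliers. Section 6.4 allows exactly these participants to be taken out of the study, not merely off ointment, and so allows the needed assessment to be lost.

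The reason behind event B is that someone who has left no longer benefits from treatment. That does not describe a participant removed administratively, who may have responded. The rule is also out of step with the rest of the protocol: a participant who asks to stop ointment altogether stays in follow-up under 7.2.1, while one who applies it irregularly can be removed under 6.4.

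At stake is whether the primary IGA/PGA comparison, and the EASI, PASI and BSA comparisons, estimate the effect the plan names. With 40 or 30 participants per arm, one lost responder changes that arm's rate by 1/40 = 2.5 points (AD) or 1/30 = 3.3 points (PsO).

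**Working it through.** **Step 1: follow one dosing record through the rules.** Take a participant whose non-compliance persists after re-training.
- Kept in the study and assessed at Week 12: event D applies, and the recorded score counts.
- Withdrawn under 6.4, with an early termination visit on Day 79 to 99: the schedule of activities includes IGA/EASI or PGA/PASI at that visit, and SAP Appendix 3 maps those days to Week 12. A score can still exist.
- Withdrawn under 6.4 before Day 79, with no later assessment: no Week 12 score exists. Event B and SAP 5.3.1 give failure (E1), and SAP 6.2.2 gives a vehicle-based imputation (E2).

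Only the third path departs from the estimand. Nothing in either document keeps participants off it.

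**Step 2: reproduce the plan's power.** Inputs are from Protocol 9.4.1 and 9.4.2.
- AD: 15% versus 50%, 40 per arm, one-sided 0.0125.
- PsO: 8% versus 50%, 30 per arm, one-sided 0.008.

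An unconditional exact test ordered by the Z statistic, with the p-value maximised over the common rate, gives 88.7% for AD (stated 89%) and 92.5% for PsO (stated 92%). Both reproduce. No attrition allowance is stated: 40 and 30 per arm appear as numbers randomized in the synopsis and as numbers completing in Table 2.

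**Step 3: effect on the difference.** Suppose fractions w1 (active) and w0 (vehicle) lose their Week 12 outcome irrespective of response and are scored as failures. The expected difference becomes p1(1 − w1) − p0(1 − w0). With k withdrawals in each arm of size n, it falls by (k/n)(p1 − p0):
- AD, k/40 × 35: 0.9, 1.75 and 2.6 points for k = 1, 2, 3.
- PsO, k/30 × 42: 1.4, 2.8 and 4.2 points for k = 1, 2, 3.

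**Step 4: range.** The shares below are assumptions; the documents give none.

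| Withdrawn without a Week 12 score | AD difference (points) | AD power | PsO difference (points) | PsO power |
|---|---|---|---|---|
| None | 35.0 | 88.7% | 42.0 | 92.5% |
| 5% in each arm | 33.3 | 85.9% | 39.9 | 90.3% |
| 10% in each arm | 31.5 | 82.7% | 37.8 | 87.6% |
| 20% in each arm | 28.0 | 75.2% | 33.6 | 80.7% |
| 10% in active only | 30.0 | 77.4% | 37.0 | 85.0% |
| 10% in vehicle only | 36.5 | 92.0% | 42.8 | 94.1% |

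The one-arm AD rows are 50 × 0.9 − 15 = 30.0 and 50 − 15 × 0.9 = 36.5.

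**The case against.** **The events do not conflict.** Event D covers non-compliers who have data; event B covers anyone whose data are missing, whatever the cause. This is right. A reader might infer that B and D contradict each other, but for a given dataset they do not. What remains is narrower: a discretionary rule can move a participant from D to B, and the estimand gives no reason for the move.

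**Withdrawal is hedged.** A reader might infer that missing two doses in a week leads to removal, since 5/7 = 71% is below the 80% threshold. Section 6.4 does not say that. The threshold leads to re-training; removal needs persistence after it and consultation with the sponsor, and is then only permitted. Sponsor involvement should also limit variation between sites, which is possible but not shown. These safeguards lower the frequency without closing the path.

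**Removal need not lose the outcome.** Also right, as Step 1 shows: an early termination visit inside the Week 12 window can supply a score. An earlier one cannot.

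**The effect may be small.** With 5% lost in each arm, power falls by only 2 to 3 points. That is fair, and it limits the weight of the point.

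**Section 6.4 has another purpose.** It is the protocol's only stated consequence for persistent non-compliance beyond re-training, and it covers over-application too. This stands, and it is why editing 6.4 alone would not be enough.

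**Conclusion.** The concern holds. Followed as written, the protocol can lose Week 12 outcomes that its own estimands require, and the analysis then replaces them with failures or vehicle-based values. It should be corrected, because the primary endpoint is affected and the remedy is cheap.

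The size cannot be derived, since the number of such withdrawals is not given. The figures above assume that withdrawal is unrelated to response and that no withdrawn participant has a score in the Week 12 window.

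Two stronger readings are tempting and unsupported. One is that the difference is necessarily biased toward zero. That follows if withdrawal is similar across arms and unrelated to response; if it falls mainly on vehicle, the difference grows. The other is that participants whose skin has cleared will apply less and so be removed more often. Protocol 6.1.1 requires cleared areas to go on being treated, but nothing in the documents says that such participants comply less.

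**What to change.** Amend Protocol 6.4 so that non-compliance alone does not end study participation. State that these participants are re-trained, that the non-compliance is recorded, and that they attend the scheduled efficacy visits through Week 12 unless they withdraw consent. Event D then applies to the scores obtained.

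Reconcile three other places in the same amendment:
- 7.1, which names only safety evaluation for participants who stop treatment, so that efficacy visits through Week 12 are covered as well;
- 7.2, so that the reasons for leaving the study agree with the amended 6.4;
- 7.2.1, so that follow-up after stopping treatment is described in the same way.

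Whether ointment is continued or stopped in a non-compliant participant, including one who over-applies, is for the sponsor to reconcile across these sections. This point proposes no rule on it.

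The cost is a small amendment touching several sections, and some poorly compliant participants remaining in follow-up for visits already in the schedule.
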